2.1 Study rationale and purpose

In various clinical trials with single agent (s.a.) oral panobinostat, it was evident that some patients may benefit from prolonged treatment with this agent well beyond the study objectives have been attained (Prince et al 2009; Duvic et al 2012; Younes et al 2012). Recognizing that it is important to allow these patients to continue their therapy under a controlled, even if less frequent monitoring plan, this multi-center, open-label roll-over protocol has been designed to better characterize the long-term safety of s.a. oral panobinostat in patients being treated in a Novartis-sponsored, Oncology OGD&GMA study who are responding to treatment with this agent.

The purpose of this study is to better characterize the long-term safety of panobinostat in patients who are on s.a. panobinostat treatment in a Novartis-sponsored, Oncology OGD&GMA study that has reached its objectives, who are not progressing on the current study treatment as defined by the parent protocol and are benefiting from this treatment as

judged by the investigator. Parent studies eligible to participate in the roll-over study will be decided by Novartis. Investigator initiated trials (IITs) will not be included. The objectives of the parent study must have been reached and the parent study must be in the process of being completed and reported.

Patients enrolled in this study will continue to receive s.a. oral panobinostat until one of the following occurs: the patient is no longer benefiting from the treatment (e.g. the underlying disease is progressing), unacceptable toxicity develops, consent is withdrawn, non-compliance with the protocol, the investigator feels it is no longer in the patient's best interest to continue therapy (e.g. pregnancy, etc.), or the patient's death.

2.2 Rationale for the study design

This is a multi-center, open-label study to better characterize the long-term safety of s.a. oral panobinostat in patients being treated in a current Novartis-sponsored, Oncology OGD&GMA study, who are benefiting from the treatment with oral panobinostat.

The design of this roll-over study is widely used in cancer clinical programs to allow access to an effective study treatment to those patients who are benefiting from this therapy well beyond trial objectives completion. The study protocol is also designed to gather long-term safety information in cancer patients who are eligible to transfer into this roll-over study. The well-known safety profile of panobinostat supports the rationale for a less frequent visit schedule more adapted to standard of care practice with monitoring focused on adverse events reporting. This will ensure not only adequate supervision of the patients' well-being but also proper regulatory reporting of relevant safety information.

2.3 Rationale for dose and regimen selection

The dose/s and regimen/s provided in this roll-over study protocol are those defined in the parent protocols for each enrolled patient. Therefore, depending on the capsule strength/s used in the parent protocol, s.a. panobinostat will be provided as 5-mg and/or 20-mg hard gelatin capsules. At the time of transition to the roll-over study, the starting dose and regimen of oral panobinostat should be the same as the last assigned dose and regimen that were given in the parent study. Dosing modifications thereafter (following the starting dose) may be done at the discretion of the investigator based upon what is in the patient's best interest.

2.4 Rationale for choice of combination drugs

[figure not shown]
Not applicable.

2.5 Rationale for choice of comparators drugs

Not applicable.

2.6 Risks and benefits

Based on the last edition of the IB, the risk/benefit assessment of panobinostat (LBH589) is considered favorable and unchanged. The risks of single agent panobinostat are well characterized by a large safety database and no significant new safety signals have emerged since previous editions of this IB. This assessment serves as a basis for the safety monitoring

of panobinostat tested in combination with other cancer agents in ongoing clinical studies. As appropriate, monitoring of patients is required in the clinical development protocols and no protocol changes have been or are planned to be made. Management of adverse events remains confined to clinical monitoring per protocol and appropriate dose and schedule modifications with supportive care as clinically indicated.

Consistent with the safety profile from the extensive experience with panobinostat single agent studies, the major toxicities associated with the active combination of panobinostat with bortezomib and dexamethasone in MM patients involved the same adverse events noted during single agent treatment. However, the overlapping toxicity, primarily hematologic, GI and constitutional in nature was apparent with respect to frequency and severity due to the combination regimen. Cardiac toxicity was unremarkable. The known toxicities could be predicted and could be effectively managed with established clinical interventions. In the context of the significant clinical benefit panobinostat provides to MM patients with limited treatment options, its tolerability is considered acceptable.

3 Objectives and endpoints

Objectives and related endpoints are described in [Table 3-1](#) below.

[figure not shown]
[figure not shown]

Table 3-1 Objectives and related endpoints

Objective	Endpoint	Analysis
Primary To evaluate long term safety data (SAEs and AEs)	Frequency and severity of AEs/SAEs	Refer to Section 10.4
Secondary To evaluate clinical benefit as assessed by the investigator	Proportion of patients with clinical benefit as assessed by the investigator at scheduled visits	Refer to Section 10.5.2

4 Study design

4.1 Description of study design

This is a multi-center, open-label study to better characterize the long-term safety of s.a. oral panobinostat in patients being treated in current Novartis-sponsored, Oncology OGD&GMA study and who are benefiting from the treatment with s.a. oral panobinostat as determined by the guidelines of the parent protocol (for which the study objectives have been met) and based on the investigator's clinical judgment.

This roll-over study will not include screening period as patients will transfer directly from the parent study and commence with panobinostat as soon as they are consented and meet inclusion criteria of the roll-over protocol. All patients must report to the study site for their first visit and commence study participation. At that time, a quarterly (12 +/- 2 weeks) supply of oral panobinostat will be dispensed to the patient or as per local practice.

Patients must return to the study center on a quarterly (every 12 +/- 2 weeks) basis for resupply of study medication at which time limited drug dispensing information will be collected. Changes in dosing which might occur any time during the study treatment will be documented on the dose administration page.

Patients may return to the study center more frequently at the physicians' discretion as clinically indicated or as per standard of care, however, these unscheduled visits will not be captured in the eCRF, but rather only in the source documents at the study center.

All adverse events and serious adverse events will be collected throughout the study.

Patients entering the roll-over protocol should be followed at the investigator's discretion for known and/or clinically notable AEs that occur on panobinostat treatment as described in the current version of the [Investigator Brochure].

Patients will continue to be treated in the roll-over protocol until they are no longer benefiting from the s.a. oral panobinostat treatment, develop unacceptable toxicities, withdraw consent, are non-compliant to the protocol, the investigator feels it is no longer in the patient's best interest to continue s.a. oral panobinostat therapy, pregnancy occurs or the patient dies, or study is terminated by sponsor, whichever comes first. At every quarterly visit, the investigator is required to confirm that the patient continues to have clinical benefit and may continue receiving study treatment.

A patient will reach the end of the study treatment when s.a. oral panobinostat treatment is permanently discontinued. A 30-day safety follow-up after last dose of study drug should be conducted.

The study is expected to remain open for 5 years or until such time that enrolled patients no longer need treatment with panobinostat, whichever occurs earlier.

[figure not shown]
[figure not shown]

Figure 4-1 Study design

4.2 Timing of interim analyses and design adaptations

No interim analyses are planned.

4.3 Definition of end of study

End of study is defined as either a 5 year duration or when all patients in this study have permanently discontinued panobinostat treatment and the end of treatment visit plus the 30-day safety follow up have been performed for each patient (and no further follow-up is needed), whichever comes earlier.

4.4 Early study termination

The study can be terminated at any time for any reason by Novartis. Should this be necessary, the patient should be seen as soon as possible and the same assessments should be performed as described in [Section 7.1.3](#). The investigator may be informed of additional procedures to be followed in order to ensure that adequate consideration is given to the protection of the patient's interests. The investigator will be responsible for informing IRBs and/or ECs of the early termination of the trial.

5 Population

5.1 Patient population

The study population is constituted of patients with various malignancies who participated in a Novartis-sponsored, Oncology OGD&GMA clinical trial for their specific indication and qualify to transfer to this roll-over protocol.

The investigator or designee must ensure that only patients who meet all the following inclusion and none of the exclusion criteria are offered treatment in the study.

5.2 Inclusion criteria

Patients eligible for inclusion in this study have to meet **all** of the following criteria:

1. Patient is currently enrolled in a Novartis-sponsored, Oncology OGD&GMA study receiving s.a. oral panobinostat and has fulfilled all their requirements in the parent study.
2. Patient is currently benefiting from the treatment with s.a. oral panobinostat as determined by the guidelines of the parent protocol and according to the Investigator's clinical judgment.

3. Patient has demonstrated compliance, as assessed by the investigator, with the parent study protocol requirements.
4. Willingness and ability to comply with scheduled visits, treatment plans and any other study procedures.
5. Written informed consent obtained prior to enrolling into the roll-over study.
 - If consent cannot be expressed in writing, it must be formally documented and witnessed, ideally via an independent trusted witness.

5.3 Exclusion criteria

Patients eligible for this study must not meet **any** of the following criteria:

1. Patient has been permanently discontinued from s.a. oral panobinostat study treatment in the parent study due to unacceptable toxicity, withdrawal of consent, non-compliance to study procedures or any other reason (including progression of disease).
2. Patient has participated in a Novartis sponsored combination trial where panobinostat was dispensed in combination with another study medication and is still receiving combination therapy.
3. Patient is pregnant or nursing (lactating) at time of entry into the roll-over protocol. Pregnancy is defined as the state of a female after conception and until the termination of gestation, confirmed by a positive hCG laboratory test.
4. Women of child-bearing potential and male patients with sexual partner(s) of child-bearing potential unwilling to use highly effective methods of contraception during dosing and for a specified duration (6 months for male participants and 3 months for females) after stopping study treatment.

Highly effective contraception methods include:

- Total abstinence (when this is in line with the preferred and usual lifestyle of the subject. Periodic abstinence (e.g., calendar, ovulation, symptothermal, post-ovulation methods) and withdrawal are not acceptable methods of contraception.
- Female sterilization (have had surgical bilateral oophorectomy with or without hysterectomy) or tubal ligation at least six weeks before taking study treatment. In case of oophorectomy alone, only when the reproductive status of the woman has been confirmed by follow up hormone level assessment.
- Male sterilization (at least 6 months prior to enrolling). For female patients on the study the vasectomized male partner should be the sole partner for that patient.
- Use of oral, injected or implanted hormonal methods of contraception or placement of an intrauterine device (IUD) or intrauterine system (IUS), or other forms of hormonal contraception that have comparable efficacy (failure rate <1%), for example hormone vaginal ring or transdermal hormone contraception. Women using hormonal contraceptives should additionally use a barrier method of contraception.

Note: In case of use of oral contraception, women should have been stable on the same pill for a minimum of 3 months before entering the roll-over protocol.

- Women are considered post-menopausal and not of child bearing potential if they have had 12 months of natural (spontaneous) amenorrhea with an appropriate clinical

profile (i.e. age appropriate, history of vasomotor symptoms) or have had surgical bilateral oophorectomy (with or without hysterectomy), total hysterectomy, or tubal ligation at least six weeks ago. In the case of oophorectomy alone, only when the reproductive status of the woman has been confirmed by follow up hormone level assessment is she considered not of child bearing potential.

- If a study patient becomes pregnant or suspects being pregnant during the study or within 30 days after the final dose of panobinostat, the Investigator/Study Doctor needs to be informed immediately and ongoing study treatment with panobinostat has to be stopped immediately.
5. Sexually active males unless they use a condom during intercourse while taking the drug during treatment and for 6 months after stopping treatment and should not father a child in this period. A condom is required to be used also by vasectomized men as well as during intercourse with a male partner in order to prevent delivery of the drug via semen.

6 Treatment

6.1 Study treatment

Study drug and investigational treatment refer to s.a. oral panobinostat (hereof defined as the study treatment).

6.1.1 Dosing regimen

Table 6-1 Dose and treatment schedule

Study treatments	Pharmaceutical form and route of administration	Strength	Dosing Regimen
Panobinostat	Capsule for oral use	5 mg, 10mg, 15mg and/or 20 mg depending on parent protocol	Per parent protocol

The dose/s and regimen/s provided in this roll-over study protocol are those defined in the parent protocols for each enrolled patient, hence this may differ for patients enrolling from various studies.

Panobinostat will initially be provided as 5 mg and/or 20 mg hard gelatin capsules, depending on the strength/s used in the parent protocol. If the need arises at a later time, also 10mg and/or 15mg capsules might be used. The investigational treatment is to be stored in a secure locked area while under the responsibility of the investigator. Receipt and dispensing of investigational treatment must be recorded by an authorized person at the investigator's site.

Patients will be instructed to take panobinostat orally with a glass of water, at the last assigned dose and schedule received in the parent protocol, either consistently with food or consistently without food. The capsule should be swallowed as a whole and should not be chewed or crushed. Dietary habits at the time of enrolling in the study from the parent study should be kept as consistent as possible throughout the study.

6.1.2 Ancillary treatments

Not applicable

6.1.3 Rescue medication

Not applicable

6.1.4 Guidelines for continuation of treatment

The starting dose of oral panobinostat should be the same as the last assigned dose and schedule that was given in the parent study. Assigned dose is the dose as designated by investigator and does not include unintended changes or error in dosing in parent protocol.

Dose modification thereafter (following the starting dose) may be done at the discretion of the investigator based upon what is in the patient's best interest.

In case patients do not tolerate the dosing schedule, dose adjustments are permitted in order to keep the patient on study drug. These dose adjustments may be delays in dosing and/or reductions in the dose being administered. Dosing should always be temporarily discontinued if the physician determines it is in the best interest of the patient. All dose modifications should be recorded in the source documents and on the Dosage Administration Record Form.

Patients receiving a reduced dose of panobinostat due to toxicity who are clearly benefiting from panobinostat and whose AE(s) remain grade $<$ or $=$ 1, which the patient believes is/are tolerable may at the discretion of the Investigator after agreement by the Sponsor return to the initial dosage in 5mg/increments. Dose re-escalation should be reviewed on a case basis and requires agreement between Sponsor and Investigator. No more than 2 dose reductions are permitted (i.e. the minimum dose patients may receive is 5 mg/day).

[figure not shown]

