6.2 Dose modifications

For patients who do not tolerate the specified dose, dose adjustments are permitted in order to allow the patient to continue treatment. The following guidelines should be applied.

If a patient requires a dose delay more than 28 days from the intended day of the next scheduled dose, the patient should be considered for discontinuation of treatment. If, however, the patient was clearly benefitting from treatment and the cause of the delay has resolved, the patient may be able to restart treatment after discussion with Novartis. This option should be used with the highest amount of caution keeping the safety of the patient in mind, and evaluating whether or not the benefit outweighs the risk.

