6.2.1 Non-Cardiac Toxicity Dose Modifications

Treatment dose and/or schedule modification may be required based on individual tolerability. Clinical judgment on how to continue the treatment should be exercised when a patient experiences adverse drug reactions.

If a dose reduction is required, the dose of panobinostat should be reduced by decrements of 5 mg (i.e. from 20 to 15 mg or from 15 to 10 mg). The dose should not be reduced below 10 mg daily and the same treatment schedule should be maintained.

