6.2.2 Thrombocytopenia

If patients experience thrombocytopenia (TCP), panobinostat may need to be temporarily withheld and the subsequent dose may need to be reduced. In patients with Common Terminology Criteria for Adverse Events version 3.0 (CTCAE) grade 3 ($<50 \times 10^9/L$, complicated by bleeding), or grade 4 ($<25 \times 10^9/L$) thrombocytopenia, panobinostat therapy should be withheld and resumed at a reduced dose upon recovery to \leq grade 2 ($\geq 50 \times 10^9/L$).

Discontinuation of treatment may be considered if thrombocytopenia does not improve despite the treatment modifications described above and/or the patient requires repeated platelet transfusions.

Table 6-2 Thrombocytopenia dose modifications

Thrombocytopenia grade on day of treatment	Modification of panobinostat starting dose	Panobinostat dose on recovery to \leq grade 2 thrombocytopenia ($\geq 50 \times 10^9/L$)
Grade 3 with bleeding Platelets $< 50 \times 10^9/L$	Omit dose	Resume at reduced dose
Grade 4 Platelets $< 25 \times 10^9/L$	Omit dose	Resume at reduced dose

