6.2.3 Gastrointestinal toxicity

Gastrointestinal toxicity is very common in patients treated with panobinostat. Patients who experience diarrhea and nausea or vomiting may require temporary dose discontinuation or dose reduction.

Table 6-3 Diarrhea dose modifications

Adverse drug reaction	Grade on day of treatment	Modification of panobinostat starting dose	Panobinostat dose on recovery to \leq grade 1
Diarrhoea	Grade 2 despite anti-diarrheal medicinal product	Omit dose	Resume at the same dose
	Grade 3 despite anti-diarrheal medicinal product	Omit dose	Resume at reduced dose
	Grade 4 despite anti-diarrheal medicinal product	Discontinue	Discontinue

At the first sign of abdominal cramping, loose stools, or onset of diarrhea, it is recommended that the patient be treated with anti-diarrheal medication (e.g. loperamide). Prophylactic antiemetics should be administered at the discretion of the physician and in accordance with local medical practice.

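### Protocol 6.1.4 allows dosing down to 5 mg/day while 6.2.1 stops at 10 mg for non-cardiac toxicity; neither takes precedence, and a recovered patient due to resume below 10 mg has no clear instruction.

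*Protocol*

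**What the plan says.** Section 6.1.4 fixes the starting dose at the last dose assigned in the parent study and leaves later changes to the investigator. In a paragraph that opens with patients whose dose was reduced for toxicity, it ends: "No more than 2 dose reductions are permitted (i.e. the minimum dose patients may receive is 5 mg/day". It does not separate cardiac from non-cardiac toxicity.

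Section 6.2 introduces its own rules with "The following guidelines should be applied". Within it, Section 6.2.1, headed for non-cardiac toxicity, sets the step: "the dose of panobinostat should be reduced by decrements of 5 mg (i.e. from 20 to 15 mg or from 15 to 10 mg". It then sets a floor: "The dose should not be reduced below 10 mg daily and the same treatment schedule should be maintained".

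The toxicity-specific sections rely on a lower dose being available. For grade 3 thrombocytopenia with bleeding, or grade 4, Section 6.2.2 says "panobinostat therapy should be withheld and resumed at a reduced dose upon recovery". Table 6-3 (grade 3 diarrhoea) and Table 6-4 (grade 4 or febrile neutropenia) use the same instruction, "Resume at reduced dose". None of these sections gives a floor of its own.

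Section 6.1.1 provides for 5, 10, 15 and 20 mg capsules, with 5 mg and/or 20 mg supplied at first. Starts at 10 or 15 mg, and a 5 mg dose, are therefore practicable.

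**The concern.** Two sections of the current protocol give different lowest doses for the same situation, and nothing ranks them. A site reading 6.1.4 could take a patient from 10 mg to 5 mg. A site reading 6.2.1 would find no lower dose allowed.

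The parenthesis in 6.1.4 also presents 5 mg/day as what two reductions amount to. With 5 mg steps that is true of one starting dose only.

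The second difficulty follows from the first. A patient who has a listed toxicity at 10 mg and then recovers is told to resume lower, but under the 6.2.1 floor there is no lower dose.

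What is at stake is consistent dosing and the safety of a few patients. The 5 mg dose is not an overexposure. The outcome to avoid is a site that keeps to the 10 mg floor and restarts at 10 mg, the dose that preceded the event. That would depart from Table 6-2, and Section 6.2.7 describes thrombocytopenia on this drug as dose-dependent. SAP Section 5.4.3.2 lists dose records and displays reasons for changes, so divergent handling would be visible afterwards but not prevented.

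**Working it through.** **Inputs**
- At most 2 reductions, minimum 5 mg/day: Protocol 6.1.4.
- Floor of 10 mg daily for non-cardiac toxicity, 5 mg decrements: Protocol 6.2.1.
- Starting dose equal to the last assigned parent-study dose: Protocol 6.1.4. Actual starting doses are not given.
- Doses of 40 and 60 mg, mentioned in Appendix 14.1.2, taken here as possible high starts.
- 9 patients enrolled and 3 ongoing: Amendment 01 rationale.

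**Assumptions**
- Reductions under 6.1.4 are also 5 mg steps. That section states 5 mg only for re-escalation.
- Reductions are counted from roll-over entry. The protocol does not say whether parent-study reductions count.

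**The plan's own figure.** The parenthesis in 6.1.4 implies start − 2 × 5 mg = 5 mg. Solving gives start = 15 mg. For a 20 mg start, 20 − 2 × 5 = 10 mg, so the stated 5 mg is reproduced only from a 15 mg start.

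**Dose sequences for non-cardiac toxicity.** The two-reduction limit is applied in both columns.

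| Start (mg) | Under 6.1.4 | Adding the 6.2.1 floor | Differ? |
|---|---|---|---|
| 60 | 60, 55, 50 | 60, 55, 50 | No |
| 40 | 40, 35, 30 | 40, 35, 30 | No |
| 20 | 20, 15, 10 | 20, 15, 10 | No |
| 15 | 15, 10, 5 | 15, 10 | At reduction 2 |
| 10 | 10, 5 | 10 | At reduction 1 |
| 5 | 5 | 5 (already below the floor) | No further reduction under either |

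**Next dose for a patient now at 10 mg**
- Started at 10 mg, 0 reductions used: 5 mg under 6.1.4, none under 6.2.1.
- Started at 15 mg, 1 used: 5 mg under 6.1.4, none under 6.2.1.
- Started at 20 mg, 2 used: none under either.

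The third route matters for the fix. Even where the floors agree, a 20 mg starter who has used both reductions has no lower dose left and meets the same table instruction.

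**Where the resume-lower instruction appears.** Table 6-2, 2 of 2 rows; Table 6-3, 1 of 3; Table 6-4, 1 of 2. Total 2 + 1 + 1 = 4 of 2 + 3 + 2 = 7 rows. This counts instructions, not patients.

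**What the stopping text covers.** Section 6.2.2 says "Discontinuation of treatment may be considered if thrombocytopenia does not improve despite the treatment modifications described above", and Section 6.2.4 has a similar sentence for neutropenia. Both concern a cytopenia that fails to improve. A patient who recovers at 10 mg and is due to resume lower falls outside them.

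**The case against.** The strongest reply is that the rules can be reconciled. Section 6.1.4 gives an outer limit, 6.2.1 gives narrower guidance for one class of toxicity, and the specific rule ordinarily governs within its scope. A site that never goes below 10 mg breaches neither floor. This is a sensible reading, but the protocol does not state it, and the 6.1.4 paragraph is itself about toxicity. Nor does it help a patient already at 10 mg whom a table tells to resume lower.

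Second, later dosing is left to the investigator, and 6.2.1 itself calls for clinical judgment, so some variation between sites is intended. That stands. Discretion does not say which floor bounds it, however, and Section 12 permits no authorized deviations.

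Third, a reader might infer that a patient at the floor has no way out. The documents do not support that. Section 6.1.4 allows temporary discontinuation whenever the physician thinks it best. Sections 6.1.5 and 7.1.5 allow stopping for unacceptable toxicity or the patient's best interest. Section 6.2 has discontinuation considered in the case "If a patient requires a dose delay more than 28 days from the intended day of the next scheduled dose". Nor does either floor authorise restarting at 10 mg after an event in Table 6-2. What remains is narrower: these are judgments, and none tells the site what to do once the patient has recovered.

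Fourth, a reader might infer that the floor for QTcF reductions is also unclear, because 6.2.6 allows a reduced dose without naming one. It is not: 6.2.1 is confined to non-cardiac toxicity, so the general 5 mg minimum in 6.1.4 is the only one that applies.

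**Conclusion.** The inconsistency is real and limited. For non-cardiac toxicity the two sections set different lowest doses with no precedence. Under the two assumptions listed in the check, they part company for 15 mg and 10 mg starters only. If 6.1.4 reductions could be of another size, or if parent-study reductions count, the affected starting doses could change, but the clash between a 5 mg and a 10 mg floor would not.

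The number of patients is unknown because starting doses are not given: 0 to 3 of those ongoing at Amendment 01, plus any later enrolees. Each would also need a qualifying toxicity at 10 mg. The study tests no hypothesis and has no sample size calculation, so nothing statistical depends on this. It should be fixed because the change is small and bears on safe dosing.

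**What to change.** Amend the protocol as follows.

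1. In 6.1.4, delete the parenthesis that derives 5 mg/day from the two-reduction limit, and keep that limit as a separate rule.
2. State one floor for non-cardiac toxicity in both 6.1.4 and 6.2.1. Use 10 mg, as 6.2.1 has it, unless the sponsor intends 5 mg. If 5 mg is chosen, note that the two-reduction limit still stops a 20 mg starter at 10 mg.
3. Add to 6.2.1, with a reference from Tables 6-2 to 6-4, that a patient who needs a reduction below the floor, or a third reduction, does not resume at the same dose and discontinues study treatment.

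Section 12.1 requires a written amendment for any change or addition, with approval by the sponsor, by health authorities where required, and by the ethics committee. The cost is that approval process. No data, visits or patients are added.

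### Section 6.1.4 treats a cap of two dose reductions and a 5 mg/day minimum as one limit, but with the 5 mg decrement of Section 6.2.1 they agree only for a 15 mg start

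*Protocol*

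**What the plan says.** Protocol Section 6.1.4 limits reductions in one sentence: "No more than 2 dose reductions are permitted (i.e. the minimum dose patients may receive is 5 mg/day". The same section takes the entry dose from the parent study: "The starting dose of oral panobinostat should be the same as the last assigned dose and schedule that was given in the parent study". Section 6.1.1 adds, of doses and regimens, "hence this may differ for patients enrolling from various studies", and Table 6-1 lists capsule strengths as "5 mg, 10mg, 15mg and/or 20 mg depending on parent protocol".

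Section 6.1.4 does not give the size of a reduction. It uses 5 mg only for going back up: "return to the initial dosage in 5mg/increments". The size of a reduction is in Section 6.2.1: "the dose of panobinostat should be reduced by decrements of 5 mg (i.e. from 20 to 15 mg or from 15 to 10 mg". The next sentence there sets a floor that differs from the one in Section 6.1.4: "The dose should not be reduced below 10 mg daily and the same treatment schedule should be maintained".

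Tables 6-2, 6-3 and 6-4 require treatment to resume at a reduced dose after certain grades of thrombocytopenia, diarrhea and neutropenia. They do not refer to the cap or to either floor.

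**The concern.** A limit on the number of steps and a limit on the dose are the same limit only if the starting dose and the step size are both fixed. Here the step is fixed and the starting dose is not, so the *i.e.* cannot hold for every patient.

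The gap becomes practical when a patient who has already used two reductions has another event for which Tables 6-2 to 6-4 call for a reduced dose. One site could read the cap as exhausted. Another could read the 5 mg/day figure as the operative limit and reduce again. Section 12 permits no authorized deviations, so the written limit has to be readable in one way only.

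Safety is the primary objective, and the SAP summarizes duration of exposure by dose regimen (Section 5.4.3.1; Appendix 16.1.9, Section 2.9). Which limit a site applies would therefore show in the recorded exposure.

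**Working it through.** **Inputs**

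- Cap: 2 reductions (Protocol 6.1.4).
- Minimum equated with the cap: 5 mg/day (Protocol 6.1.4).
- Size of one reduction: 5 mg (Protocol 6.2.1).
- Second floor: 10 mg daily (Protocol 6.2.1).
- Starting dose S: not fixed; it is the last dose assigned in the parent study (Protocol 6.1.4). The values of S below are assumptions. The documents give no roll-over patient's starting dose. 20 mg is one of the two strengths supplied initially (Section 6.1.1) and the top of the example in Section 6.2.1. 10 and 15 mg are capsule strengths in Table 6-1.

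**Step 1. Reproduce the plan's figure.** Dose after two reductions = S − 2 × 5 = S − 10. Setting S − 10 = 5 gives S = 15 mg, the only solution. The stated 5 mg/day is reproduced for that start and no other.

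**Step 2. Other starts.** Reductions needed to reach 5 mg = (S − 5)/5.

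| Assumed start (mg) | S − 10 (mg) | Reductions to reach 5 mg | Cap and 5 mg minimum agree? |
|---|---|---|---|
| 10 | 0 (barred by the stated minimum) | 1 | No: the minimum binds first |
| 15 | 5 | 2 | Yes |
| 20 | 10 | 3 | No: the cap binds first |

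The example in Section 6.2.1 shows the same thing. It steps from 20 to 15 mg and from 15 to 10 mg; a patient who takes both steps has used both reductions and stands at 10 mg, not 5 mg.

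**Step 3. Would another step size rescue the sentence?** For a constant step d, S − 2d = 5 gives S = 5 + 2d, so any constant step fits exactly one start. A 10 mg step fits only S = 25 mg. From 20 mg the step would have to be (20 − 5)/2 = 7.5 mg, which is not a multiple of 5 mg. An unequal path of 20 to 10 to 5 mg meets both limits but breaks the 5 mg decrement.

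**Step 4. Would settling the floor be enough?** For a floor F, cap and floor agree when S − 10 = F, that is S = F + 10. With F = 5 this is 15 mg; with F = 10 it is 20 mg. Either floor leaves agreement at one start only.

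**The case against.** The strongest reply is that both limits can be obeyed together: at most two steps, and never below the minimum. A 20 mg starter would then stop reducing at 10 mg and a 10 mg starter at 5 mg. This is workable, and it shows that the 0 mg in the table is not an outcome the text allows. But it is not what the sentence says. The *i.e.* makes the limits one, and nothing states that the stricter governs.

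A reader might infer that the sentence contradicts itself. It does not. It gives no reduction size, and the mismatch appears only when it is read with Section 6.2.1. That link also means the point overlaps with the conflict between the 5 mg and 10 mg floors, although step 4 shows that settling the floor does not remove it.

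A reader might also infer that reaching the cap forces a patient off treatment. No section says so. Nor should the doses of 40 and 60 mg mentioned elsewhere (Section 6.2.7, Appendix 14.1.2) be used to enlarge the gap: they describe earlier experience with the drug and are not given as starting doses in this study.

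On counting, Section 6.1.4 speaks of modification after the starting dose, which suggests that the count begins at roll-over entry. It does not say so, and it does not say whether reductions made in the parent study count.

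Finally, the scale is small. Amendment 01 reports 9 patients enrolled and 3 ongoing, no hypothesis is tested, dosing after entry is largely at the investigator's discretion, and the SAP lists dose records with reasons for change. All of this stands and limits the weight of the point. General discretion does not, however, make a specific limit readable.

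**Conclusion.** The point holds as an inconsistency between Sections 6.1.4 and 6.2.1. With 5 mg decrements, two reductions and a 5 mg/day minimum coincide only at a 15 mg start. From 20 mg they differ by one reduction (a 10 mg endpoint against 5 mg); from 10 mg the minimum is reached one reduction before the cap. With the 10 mg floor the single point of agreement moves to 20 mg.

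This rests on the printed decrement and on starting doses varying as Section 6.1.1 allows; the 10 and 20 mg starts are assumed. The documents do not show that any enrolled patient was near a second reduction. The SAP contains no dose-reduction rule, and no statistical figure changes. The consequence is possible inconsistent handling, and hence inconsistent recorded exposure, in a small study with a safety primary objective. It should be corrected, but it does not threaten the analysis.

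**What to change.** The sponsor should reconcile the cap, the minimum dose and the decrement across Sections 6.1.4 and 6.2.1, including the two different floors, so that together they give one consistent limit for every starting dose that can enter from a parent study. The text should also make clear from which dose reductions are counted. The values and the governing rule are for the sponsor's clinical team; none is proposed here.

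The cost is a short wording change. Under Section 12.1 it needs a written amendment with the usual approvals. It needs no extra patients or data, and no change to the SAP.
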